3.2 Study Design

Male participants (n=15) will be recruited to ingest a tomato pomace extract once daily for 5-days across three different doses. In week one, five participants will ingest 1.0 g of extract per day for 5 days. In week two, the next five participants will ingest 2.5 g of extract per day, for five days. In week three, the next five participants will ingest 10 g extract per day, for five days. The 1.0 and 2.5 g doses of extract are the same doses we intend to investigate in phase 2. Tolerability of the tomato pomace ingestion will be assessed by physical measurements (blood pressure and pulse rate) and a gastro-intestinal well-being assessment before ingestion, and then again

3-h after ingestion of the tomato pomace extract on each of the 5 treatment days. The blood test for full blood count and biochemical profile undertaken at clinical screening (section 3.6) will form part of the baseline assessment profile. The same blood tests will be repeated 24-h after the last treatment on day 5. Figure 1 is a schematic overview of the study.

Eligibili asses	sment I	Day 1 Day 2	Day 3	Day 4	Day	5 Day 6
	Maximum 2-weeks					
		t= 0-h; Blood p intestina	oressure, pulse al well-being qu		8	
Consent Health questionnaire		Ingestio	n of treatment	dose.		
		t=3-h; Blood pressure, pulse rate, gastro- intestinal well-being questionnaire				Blood pressure, pulse rate, gastro-intestinal well being questionnal
Blood pressure, pulse, height, weight		intestin	ar weir being q	acodonnanc		5 ,
						Fasted blood sample
-						(Full blood count and
	ed blood sample					biochemical profile)
	blood count and hemical profile)					

Figure 1. Schematic overview of phase 1

- 3.3 Inclusion criteria
 - Apparently healthy men aged between 18 and 26 years
 - BMI >19.5 and < 26.0
- 3.4 Exclusion criteria
 - Known tomato allergy
 - Chronic medical conditions requiring active treatment (e.g. Cardiovascular disease, diabetes, asthma)
 - Medically or self-prescribed medication
 - Kidney or liver disease/disorders
 - Gastro-intestinal disease/disorders
 - Smokers
 - Parallel participation in another research project which involves dietary intervention
 - Depressed or elevated blood pressure measurements (<90/50 or 95/55 if symptomatic or ≥160/100 (mmHg)
 - Any person related to or living with any member of the study team

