3.8 Intervention procedure

Participants may maintain normal dietary habits during the 5-day intervention period but will be instructed to refrain from drinking any alcohol. The format for phase 1 is intended to reflect the phase 2 study and is described below.

Week 1: 5 participants will start on the lowest dose of tomato pomace extract being tested (1.0 g). Participants will arrive at the research facility on the morning of each of the 5 treatment days after fasting from 10pm the night before. During the fasting period, the participant may drink as much water as he needs. At the start of each treatment day, the research nurse will record pulse rate and blood pressure and complete a gastro-intestinal well-being questionnaire (Annex 6). The participant will then ingest the tomato pomace extract. 3-h post ingestion of the extract, the research nurse will once again record pulse rate and blood pressure and complete another gastro-intestinal well-being questionnaire after which the participant may eat and drink as normal. The participant will then be free to leave the research facility with instructions to return the following morning to repeat the procedure. 24-h after the final treatment on day 5, another 10 mL fasted blood sample will be obtained for full blood count and biochemical assessment as described in the clinical screening section of this protocol (section 3.6).

Week 2: If no problems occur after 5-days ingestion at the lowest dose tested (see section 3.9 for criteria) then the next 5 participants will ingest the next incremental dose (2.5 g). The same procedure described for week 1 above, will be followed.

Week 3: If no problems occur in week 2 (section 3.9), then the last 5 participants will ingest the highest dose of extract (10 g). The same procedure described for week 1 above will be followed.

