3.9 Stop criteria for dose escalation

Blood tests will be assessed (by a medical doctor) for abnormal variations at the end of the intervention period by comparison with the test results obtained at clinical screening. Similarly the CI will evaluate the results from the gastro-intestinal wellbeing questionnaires. Table 1 is the STOP criteria in the event that abnormal variations in blood test results and/or gastro-intestinal problems occur.

Dose extract (g)	Previous dose outcome	Abnormal at current dosing	Next step	Abnormal at re-test	Next step
		$\leq 2^{(a)}$	Escalate to next dose	n/a	n/a
1.0	N/A	≥3	Replace and re-test	0-1 ^(b)	Escalate to next dose
				≥ 2	STOP

 Table 1 Stop criteria for phase 1

Version 1 Study protocol

	All normal	≤ 2	Escalate to next dose	n/a	n/a
		≥ 3	Replace and re-test	0-1	Escalate to next dose
2.5				≥ 2	STOP
2.3	1-2 abnormal ^(a)	≤ 2	Escalate to next dose	n/a	n/a
		≥ 3	STOP	n/a	n/a
	\geq 3 abnormal ^(b)	≥2	STOP	n/a	n/a
	Any	0	Proceed to phase 2	n/a	n/a
10		1-2	Replace and re-test	0	Proceed to phase 2
				1-2	STOP
		≥3	STOP	n/a	n/a
1		1			

n/a - Not applicable; STOP - the dose-escalation study should be terminated.

If evaluation of the data indicates that the pomace extract is well tolerated at the highest dose tested, we will move onto the phase two efficacy trial.

[name] (CI) will assume responsibility for the dose escalation procedures and the decision to move into the phase two efficacy trial.

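### Table 1 judges a re-test on its own count and opens Phase 2 whatever the 2.5 g record, so 6 of 10 men abnormal at Phase 2's top dose need not stop the programme

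*Combined protocol and SAP*

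**What the plan says.** Section 3.2 plans one cohort of five men per dose. For the first cohort it says "In week one, five participants will ingest 1.0 g of extract per day for 5 days"; the second cohort is described as "In week two, the next five participants will ingest 2.5 g of extract per day, for five days"; and the third as "In week three, the next five participants will ingest 10 g extract per day, for five days". It adds that "The 1.0 and 2.5 g doses of extract are the same doses we intend to investigate in phase 2".

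Table 1 in section 3.9 gives the next step after each cohort:

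- **1.0 g, and 2.5 g after an all-normal 1.0 g cohort.** Up to 2 abnormal escalates. Three or more leads to a re-test. For the 2.5 g row the table continues "Replace and re-test 0-1 Escalate to next dose", and 2 or more at re-test stops.
- **2.5 g after a 1.0 g cohort with 3 or more abnormal (marker b).** Two or more stops, with no re-test.
- **10 g.** The row reads "Any 0 Proceed to phase 2 n/a n/a". One or two abnormal leads to a re-test, which must show 0 for Phase 2 to open. Three or more stops.

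The text after the table says "If evaluation of the data indicates that the pomace extract is well tolerated at the highest dose tested, we will move onto the phase two", and makes the chief investigator responsible for that decision. The number of men in a re-test is not stated.

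**The concern.** Phase 1 exists to establish that the extract is tolerable enough to give to Phase 2 participants. Section 4.3 plans 33 men per group, so 33 men would receive 2.5 g. Two features of Table 1 leave collected data out of that judgement.

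First, once a re-test is triggered, no cell uses the count from the cohort that triggered it. Second, the row that opens Phase 2 does not distinguish between the 2.5 g records that lead into it, and the sentence after the table looks only at the highest dose. A tolerability claim could then be made after setting aside the cohort that raised the doubt, at a dose that Phase 2 will use.

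The table does not treat this consistently. Marker (b) makes the 2.5 g row stricter after a failed 1.0 g cohort, even when the re-test was good. The authors thus regarded a failed first cohort as still relevant. Nothing equivalent links a failed 2.5 g cohort to the 10 g step or to Phase 2.

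**Working it through.** The plan states no error rate or pooled rate for Table 1, so there is no figure to reproduce. The inputs are five men per cohort (3.2) and the cut-offs in Table 1 (3.9). The per-man abnormality rate p and the re-test size are assumptions, because the plan gives neither.

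**1. Path to Phase 2.**
- 1.0 g: 0/5 abnormal, so escalate to the all-normal 2.5 g row.
- 2.5 g: 5/5 abnormal, so re-test; 1 abnormal at re-test, so escalate. Total 5 + 1 = 6 of 10.
- 10 g: 0/5 abnormal with any previous outcome, so Phase 2 opens.

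This holds whether the re-test takes five new men or replaces only the abnormal men, since all five were abnormal. Six of 10 is the largest 2.5 g total that can get through.

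**2. Does the decision follow the total?** It depends on the re-test size.

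| Sequence | Next step | Five new men | Only abnormal men replaced |
|---|---|---|---|
| Low dose, 5 then 1 | escalate | 6/10 = 60% | 6/10 = 60% |
| Low dose, 3 then 2 | stop | 5/10 = 50% | 5/8 = 62.5% |
| 10 g, 2 then 0 | open Phase 2 | 2/10 = 20% | 2/7 = 29% |
| 10 g, 1 then 1 | stop | 2/10 = 20% | 2/6 = 33% |

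With five new men the rule is not monotone. If only abnormal men are replaced, the reversal by rate disappears. Even with five new men, a total of 5 of 10 stops only as 3 then 2; 4 then 1 and 5 then 0 escalate.

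**3. How likely is the extreme path?** P(5/5 then 1/5) = p⁵ × 5p(1−p)⁴. Its maximum is at p = 0.6: 0.07776 × 0.0768 = 0.0060, or 0.6%. The chance of clearing 10 g is (1−p)⁵ + [5p(1−p)⁴ + 10p²(1−p)³](1−p)⁵. With 1.0 g taken as all normal and the same p at 2.5 and 10 g:
- p = 0.4: 0.00265 × 0.1248 = 0.00033 (0.03%), close to the maximum
- p = 0.6: 0.00597 × 0.0134 = 0.00008

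If 10 g is cleared as 2/5 then 0/5, and each dose has its own most favourable rate (0.6 and 0.2), the result is 0.00597 × 0.0671 = 0.0004, or 0.04%. If 10 g were better tolerated than 2.5 g, the only firm ceiling for the path is the 0.6%.

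**4. How likely is escalation by any re-test route at a low dose?** With five new men this is P(X≥3) × P(X≤1), X binomial with n = 5:
- p = 0.2: 0.0579 × 0.7373 = 0.043
- p = 0.3: 0.1631 × 0.5282 = 0.086
- p = 0.4: 0.3174 × 0.3370 = 0.107
- p = 0.5: 0.5000 × 0.1875 = 0.094

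If only the abnormal men are replaced, the re-test has 3, 4 or 5 men:
- p = 0.2: 0.0512 × 0.896 + 0.0064 × 0.8192 + 0.00032 × 0.7373 = 0.051
- p = 0.5: 0.3125 × 0.5 + 0.15625 × 0.3125 + 0.03125 × 0.1875 = 0.211

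**5. What the tolerability statement would rest on.** These are exact one-sided 95% upper bounds, the p at which the chance of so few abnormal men is 0.05:
- last cohort alone, 1/5: (1−p)⁵ + 5p(1−p)⁴ = 0.05 gives p = 0.66
- all men at the dose, 6/10: P(X≤6 | n = 10) = 0.05 gives p = 0.85

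The point estimates are 20% and 60%.

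**The case against.** A re-test in fresh men under a tighter cut-off (at most 1, against at most 2 in the first cohort) is a legitimate design, and it partly compensates for not pooling. Earlier results are also not ignored. The previous-outcome entry in the 10 g row covers only 2.5 g results that the table has already let through, and 10 g is four times Phase 2's top dose with a stricter requirement. A medical doctor reviews the blood tests and the chief investigator decides. The printed table is broken across a page and shows no text for markers (a) and (b), so a note may have been lost. All of this stands. It limits the point but does not remove it, since nothing legible in section 3.9 tells anyone to combine the cohorts at a dose or to weigh a failed 2.5 g cohort again.

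Three stronger readings are tempting and are not supported:

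- *That 6 of 10 passes while 5 of 10 stops, as a settled fact.* This needs a five-man re-test, which the plan does not state.
- *That the re-test rule makes escalation likely when tolerance is poor.* At a 40% rate a low-dose step escalates with probability 0.683 + 0.107 = 0.790, and at 50% with 0.500 + 0.094 = 0.594. Most of each figure comes from the first-cohort rule. Likewise, the 45% upper bound for 0/5 reflects five men, not the re-test.
- *That section 3.8 contradicts Table 1.* Its condition for going up a dose is worded "If no problems occur after 5-days ingestion at the lowest dose tested (see section 3.9 for criteria) then the next 5 participants will ingest", and so it defers to section 3.9. The wording is loose, given that up to 2 of 5 abnormal escalates, but this is secondary.

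**Conclusion.** The point holds as a gap in the rule's logic. As printed, 6 of 10 abnormal at 2.5 g does not prevent Phase 2 from opening, under either reading of the re-test. The table is also inconsistent with itself, because it carries a failed first cohort forward from 1.0 g but not from 2.5 g. That reading takes marker (b) as the link between the two rows, which the matching superscripts indicate.

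Non-monotonicity is conditional on a five-man re-test. The extreme path is rare, so the practical weight lies in the re-test route at a low dose: about 4% to 11% with five new men, or 5% at a 20% rate and 21% at a 50% rate if only abnormal men are replaced. These figures assume independent men with a common rate. The correction is worth making because it is cheap and changes what Phase 1 can claim; it does not show that Phase 1 is likely to reach a wrong answer.

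**What to change.** Before Phase 1 starts, the medical doctor and investigators should:

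1. reconcile the rows of Table 1 with each other and with the tolerability sentence that follows it;
2. state how many men a re-test includes and whether they are all new;
3. state how first-cohort and re-test results at the same dose, and the results at 1.0 and 2.5 g, bear on opening Phase 2.

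The content of those rules is theirs to set; no threshold or escalation rule is proposed here.

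For the statistical report, base the tolerability conclusion on the cumulative abnormal count among all men dosed at each dose, with its exact 95% upper bound, and not on the last cohort alone.

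The cost is a revised table, a sentence or two in section 3.9, and an amendment notified to the ethics committee. The change itself needs no extra men or procedures. The downside is a less favourable tolerability statement after a bad first cohort. Stating the re-test size will also show that the 15 men in sections 3.2 and 3.5 allow for no re-test: with two five-man re-tests the total would be 15 + 2 × 5 = 25.

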3.10 Participant randomization

Participants in this ascending dose human tolerance study will ingest 1, 2.5 or 10 g tomato pomace incorporated into a drink, over a 5 day period. Each treatment will be assigned a letter (A-C). Once all 15 participants have been recruited they will be block randomized to treatment by the computer programme randomization.com. The participants will be blinded to the treatment dose.

3.11 Participant payment

Each participant will receive an inconvenience allowance of 15,000 Chilean Peso upon completion of the study or pro-rata for non-completion.

4. PHASE 2 – The Effects of ingesting a tomato pomace extract on platelet aggregation

Upon successful completion of the preliminary ascending human dose tolerance study we will conduct a parallel design human intervention trial to investigate the effects of ingesting a tomato pomace extract on platelet aggregation.

4.1 Study hypothesis

Daily ingestion of a tomato pomace extract for 5 days will significantly reduce platelet aggregation in humans compared with a placebo control and in a dose dependent manner.

4.2 Study Objectives

- 1) To determine the acute effect of ingesting two different doses of a tomato pomace extract on platelet aggregation
- 2) To determine the longer term effect of ingesting two different doses of a tomato pomace extract on platelet aggregation

4.3 Study design

A single blind, parallel design (3-groups), placebo controlled trial will be conducted to assess the acute and longer term effects of ingesting a tomato pomace extract on platelet aggregation. Participants will be randomized to receive either: a) 1.0 g tomato pomace extract delivered in flavoured water b) 2.5 g tomato pomace extract delivered in flavoured water or c) Flavoured water (placebo control). A total of 99 people are required to complete (n=33/group). Each group will ingest either a treatment or placebo once daily, for 5-days. For 14-days preceding the baseline assessment day and for the 5-day period of intervention, participants will completely exclude from the diet some foods/beverages that are known to affect platelet function (tomato and all tomato based products, alcohol, cocoa and cocoa products and green tea). To assess the acute effects of the intervention on platelet aggregation, a blood sample will be obtained before ingestion (D15; 0-h) and post ingestion (D15; 3-h) of the treatment. To assess the longer term effects, further blood samples will be taken at the end of the intervention period (D19; 0 and 3-h). Figure 2 is a schematic overview of phase 2.

[figure not shown]

Figure 2. Schematic overview of phase 2

- 4.4 Inclusion criteria
- Apparently healthy men aged between 18 and 26 years
- BMI >19.5 and <26.0

• Platelet aggregation response corresponding to $\geq 65\%$

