Day 19 – Participants will return to the research facility on the morning of day 19 having fasted from 10 pm the night before. Prior to conducting any clinical procedures the participant will again be asked some basic health related questions (Annex 9) for the reasons already described. A blood sample (15 mL) will be collected by venepuncture. The participant will once again ingest the allocated

treatment drink and a further fasted blood sample (15 mL) collected 3-h later. This completes participation in the trial.

In the unlikely event that a participant is unable to attend the pre-scheduled assessment days (e.g. minor illness) they will be given the opportunity to repeat the treatment at a later date. The total blood volume collected from each participant is 85 ml (incl. screening sample).

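### The day-19 3-h sample, assigned to the longer-term objective, also carries that day's acute effect, and no analysis is specified to separate the two

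*Combined protocol and SAP*

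**What the plan says.** Section 4.2 of the protocol lists two objectives for phase 2. The first is the acute effect. The second is "To determine the longer term effect of ingesting two different doses of a tomato pomace extract on platelet aggregation", and the term is not defined further.

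Section 4.3 assigns samples to each. For the acute effect, "a blood sample will be obtained before ingestion (D15; 0-h) and post ingestion (D15; 3-h) of the treatment". For the other objective, "To assess the longer term effects, further blood samples will be taken at the end of the intervention period (D19; 0 and 3-h".

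Section 4.10 gives the order of events on day 19. First, "A blood sample (15 mL) will be collected by venepuncture". Then "The participant will once again ingest the allocated" "treatment drink and a further fasted blood sample (15 mL) collected 3-h later". The fifth drink therefore falls between the two D19 samples.

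The hypothesis in section 4.1 is about the whole regimen: "Daily ingestion of a tomato pomace extract for 5 days will significantly reduce platelet aggregation". It names no sampling time.

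Section 4.14 names the primary outcome as platelet aggregation and the method as a one-way between-subjects ANOVA or Kruskal–Wallis test, followed by Tukey's HSD. It gives no day, hour, change score, baseline adjustment or contrast for either objective.

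**The concern.** A one-way between-subjects ANOVA takes one value per man. Each man supplies four samples, so someone must choose which sample, or which difference, answers objective 2. Section 4.3 makes D19 3-h an eligible choice. It is also a natural one, because it is the only sample taken after all five doses, and section 4.1 speaks of five days of intake.

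That sample is drawn at the same interval after a drink as the D15 3-h sample used for objective 1. If the extract lowers aggregation for a few hours and the effect is gone by the next morning, the D19 3-h comparison with placebo will still show it. Without a stated contrast, the result could be presented as evidence that repeated intake produces something beyond the response to a single drink.

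**Working it through.** **Inputs from section 4.14.** Difference from control 17.4 at 2.5 g and half of that, 8.7, at 1.0 g; SD 19.5; 5% significance; 90% power; 33 completers per group. I read the percentages as points of aggregation.

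**Step 1: reproduce the plan's figure.** For a three-group F test the noncentrality is λ = n × Σ(mean − grand mean)² / SD². The group means 0, −8.7 and −17.4 have grand mean −8.7, so the sum of squares is 2 × 8.7² = 151.38, and SD² = 380.25.

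- n = 33: λ = 33 × 151.38 / 380.25 = 13.14, with 2 and 96 degrees of freedom; power 90.2%.
- n = 32: power 89.2%.

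So 33 per group is the smallest number that reaches 90%, and the stated sample size is reproduced.

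**Step 2: what each sample contains.**

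| Sample | Doses before it | Same-day dose effect included? |
|---|---|---|
| D15 0-h | 0 | no (baseline) |
| D15 3-h | 1 | yes |
| D19 0-h | 4 (D15–D18) | no |
| D19 3-h | 5 | yes |

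**Step 3: a purely acute effect.** Assume that the planning effect appears 3 h after the drink on both days and is absent at D19 0-h. Assume also SD 19.5 at every sample, and a common within-person correlation r. The documents give no r, so values of 0, 0.5 and 0.8 were used. In 20,000 simulated trials with 33 per group, the F test offered as evidence for the longer-term objective rejected as follows:

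| Response analysed | r = 0 | r = 0.5 | r = 0.8 |
|---|---|---|---|
| D19 3-h | 90% | 90% | 90% |
| D19 3-h minus D15 0-h | 61% | 90% | >99% |
| D19 0-h | 5% | 5% | 5% |
| D19 0-h minus D15 0-h | 5% | 5% | 5% |
| D19 3-h minus D15 3-h | 5% | 5% | 5% |

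The first row is the step 1 calculation again, because the assumed effect at 3 h is the planning effect. The second row follows from the SD of a change, 19.5 × √(2(1 − r)). This gives λ = 6.57, 13.14 and 32.84, hence 61%, 90% and >99%. Taking a change from baseline therefore does not remove the acute component from D19 3-h, and with high correlation it makes a rejection more likely.

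**Step 4: a smaller acute effect.** With half the planning effect (0/4.35/8.7), λ = 13.14 / 4 = 3.28, and D19 3-h alone still rejects in about 34% of trials.

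**The case against.** The case for the plan has four parts.

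- *Section 4.3 is a sampling schedule, not a test.* It does not say that D19 3-h alone will be the longer-term endpoint. A reader might infer that an acute effect would be reported as longer term. The documents do not support that; they only leave it open. This part stands.
- *The design can separate the effects.* There are pre-dose and 3-h samples on both days, with a concurrent placebo group. A reader might infer that the two objectives cannot be told apart. That is wrong: D19 0-h does it, and so does D19 3-h set against D15 3-h, which uses the criticised sample and rejects at the nominal 5% when the effect is purely acute. What is missing is the statement of which contrast will be used.
- *D19 3-h is a valid randomised comparison.* It measures the regimen after all five doses and is the sample that best matches section 4.1, whereas D19 0-h follows only four. This also stands, and the sample should be kept and reported. It does not make D19 3-h alone evidence for an objective that section 4.2 lists separately from the acute one.
- *The 90% is the plan's own power moved to another time point.* This is correct. It illustrates one scenario, that the planning effect is wholly acute, and the documents give no evidence for or against that.

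**Conclusion.** The concern holds as a gap between objective, sample and analysis. Section 4.3 assigns to the longer-term objective a sample that combines a same-day effect with any effect of repeated intake, and section 4.14 names no analysis that separates them. A purely acute effect could therefore be reported as longer term. In the scenario tested, an ANOVA on D19 3-h rejects in about 90% of trials, against about 5% for D19 0-h or for the D19 3-h minus D15 3-h change.

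These figures assume an acute effect of the planning size that is gone by the next morning, and equal SDs at all samples. The within-person correlation is also assumed, but of the responses tested it changes the result only for D19 3-h minus D15 0-h.

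A reader might also infer a sample-size error. There is none: 33 per group reproduces. The same number gives 90.2% power at D19 0-h if the planning effect and SD hold there, which the documents do not state.

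**What to change.** In sections 4.3 and 4.14, tie each objective to one analysis:

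1. **Objective 1 (acute):** D15 3-h by group, adjusted for D15 0-h (ANCOVA).
2. **Objective 2 (longer term):** D19 0-h by group, adjusted for D15 0-h, described as the effect before the fifth dose, after four daily doses.
3. **Combined effect:** D19 3-h by group, adjusted for D15 0-h, reported as the same-day plus repeated-dose effect after all five doses and identified as the sample that matches the 5-day hypothesis in section 4.1.
4. **Change in response:** D19 3-h versus D15 3-h, to show whether the response changes with repeated intake.
5. State that D19 3-h alone will not be used to support a longer-term claim.

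All four samples are already collected and the number of participants does not change. The change is more than wording, because it replaces an unadjusted ANOVA with an adjusted one and fixes what objective 2 means. The price is a narrower longer-term claim and one more contrast to report.
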